11.1 Sample Size & Stopping Rules

Incurable groin recurrence has a >90% mortality within 12 months [21]. We estimate the probability of incurable groin recurrence within 12-month of an upfront LND, i.e., $P(\text{recur}|\text{LND})$, to plausibly be up to 3% in usual practice. This is based on a 32% prevalence of positive nodes in clinical stage I/II vulva cancer [41] and that the false negative rate for routinely used SNB is up to 8.8% [7,42]. A

recurrence probability given groin USM, i.e., $P(\text{recur}|\text{USM})$, of 6% would be acceptable to avoid the side-effects of LND based on our decision analysis using best available evidence, expert judgement, and consumer input. $P(\text{recur}|\text{USM})$ will be characterised using a Bayesian Beta-Binomial model with priors informed by our pilot study (1/32 recurrences) [10]. We will declare groin USM acceptably safe if the probability that $P(\text{recur}|\text{USM}) < 0.06$ is 80%. A Bayesian Monitoring approach will ensure participant safety (MD Anderson Biostatistics BTOX routine www.trialdesign.org/#software). Stopping early due to unacceptably safety will be triggered if there is more than a 70% probability that $P(\text{recur}|\text{USM})$ exceeds 0.06 (i.e., recurrence rate of at least 5/40, 6/60, 7/80, 9/100, or 10/120). We anticipate that $P(\text{recur}|\text{USM})$ is truly 3% and thus calculate that ANVU has less than a 2% probability of incorrectly stopping early for unacceptable safety and a 0.85 probability of correctly declaring acceptable safety at N=120. The statistical design accommodates expansion beyond N=120 USM participants (e.g., as a protocol amendment) if neither safety criterion is reached and the predicted probability of success given expansion is at least 80%.

11.2 Statistical Analysis

Analyses will adhere to the intention-to-treat principle and a Statistical Analysis Plan will be prepared using the estimand framework (ICH E9-R1 addendum).

11.2.1 Incidence of Enlarged, Palpable Groin Nodes

Groin USM will be deemed acceptably safe if the probability that $P(\text{recur}|\text{USM}) < 0.06$ is 80% using the approach described [in section 11.1](#). This will be supplemented by conventional frequentist methods to estimate the proportion of women with clinically enlarged palpable groin node metastases at 12 months from randomisation for each group together with 95% confidence intervals. The difference in proportions between groups will also be calculated and presented with confidence intervals.

11.2.2 Impact of Ultrasound Surveillance on Quality of Life and Function, Pain, Lymphoedema and Morbidity

Demographics, behavioural characteristics and comorbidities will be captured at enrolment (baseline), 8 weeks, 6 months and 12 months, PROMs including HRQL and FoR (only at 12 months) will be assessed by a study-specific survey incorporating validated instruments:

PROMs will be scored according to their manuals to construct scales. Comparisons between randomised groups on PROMs scales will be performed using a linear mixed model for repeated measures accounting for stratification factors. Analysis will also be performed using a time-integrated approach to HRQL outcomes assessment pioneered by [name] [44]. Logistic regression will be used to compare groups on categorical outcomes (or an exact test if there are few events). Categorical outcomes include: return to usual activities at 8 weeks post-surgery; and the proportion of women experience a clinical relevant change in PROMs from baseline [45] at 8-weeks post-surgery, 6 months post-surgery, and 12 months post-surgery.

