|-------------------------------------------------------|--------------------------------------------------------------------------------------------------------------------------------------------------------------------------------------------------------------------------------------------------------------------------------------------------------------------------------------------------------------------------------------------------------------------------------------------------------------------------------------------------------------------------------------------------------------------------------------------------------------------------------------------------------------------------------------------------------------------------------------------------------------------------------------------------------------------------------------------------------------------------------------------------------------------------------------------------------------------------------------------------------------------------------------------------------------------------------------------------------------------------------------------------------------------------------------------------------------------------------------------------------------------------------------------------------------------------------------------------------------------------------------------------------------------------------------------------------------------------------------------------------------------------------------------------------------------------------------------------|
| | 
 • bilateral groin USM every 2 months (groin lymph nodes are not removed) in conjunction with clinical examinations every 3 months for a period of 12 months 
OR
 
 • groin LND (based on clinical standards: either a sentinel node biopsy (SNB) or an inguinofemoral lymph node dissection (IFL)), 
Randomisation will be stratified by clinical stage, HPV status, Charlson Comorbidity Index, and histological cell type.
 |

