8.1 EuroQoL-5D (EQ-5D)

The EQ-5D is one of the most frequently used generic, preference-based instruments for measuring the health utilities of patients in economic evaluations [37]. EQ-5D is a standardised instrument for use as a measure of health outcomes. It provides a descriptive profile and a single index value for health status. EQ-5D will measure changes in health status and quality of life to calculate the quality-adjusted life years (QALYs) gained with the intervention. The EQ-5D will be administered at baseline, 8 weeks, 6 months, and 12 months. This valid HRQL tool is also a utility measure in cost-effectiveness studies. For our short-term primary outcome, we will specifically focus on return to usual daily activities specified in the EQ-5D-5L with 5 levels (unable to do, severe-, moderate-, slight-, or no-restrictions), as consumers in our focus groups rated it as most relevant.

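### Section 11.2.2 names adjustment for the PROM mixed model but none for the logistic comparisons of categorical outcomes, although baseline values and strata will be in hand; adding them costs nothing and gains a modest amount of power

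*Protocol*

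**What the plan says.** Section 11.2.2 gives two analysis rules in consecutive sentences on model choice.

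- PROM scales: "Comparisons between randomised groups on PROMs scales will be performed using a linear mixed model for repeated measures accounting for stratification factors".
- Categorical outcomes: "Logistic regression will be used to compare groups on categorical outcomes (or an exact test if there are few events".

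Two kinds of categorical outcome follow. One is the 8-week item ("Categorical outcomes include: return to usual activities at 8 weeks post-surgery"). The other is a responder outcome at 8 weeks, 6 months and 12 months ("the proportion of women experience a clinical relevant change in PROMs from baseline").

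Section 8.1 gives the first of these some prominence: "For our short-term primary outcome, we will specifically focus on return to usual daily activities specified in the EQ-5D-5L with 5 levels". The same section fixes the measurement times: "The EQ-5D will be administered at baseline, 8 weeks, 6 months, and 12 months". The pre-surgical level of the item will therefore be known. The synopsis says: "Randomisation will be stratified by clinical stage, HPV status, Charlson Comorbidity Index, and histological cell type". Section 6.4 gives the levels: three bands of depth of invasion for clinical stage, and two levels each for HPV status, Charlson index and cell type.

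Section 11.2 says a statistical analysis plan will be prepared.

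**The concern.** Adjustment is stated for one model and not for the next, within one paragraph. A programmer or SAP author who follows the text literally would fit the logistic model with treatment alone. The exact-test fallback would normally carry no covariates at all.

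Two things are then left unused. The first is the baseline value of the same item or scale, usually the strongest available predictor of the follow-up value; a return to usual activities also presupposes a pre-surgical level. The second is the set of stratification factors. Ignoring them makes the categorical analyses inconsistent with both the randomisation and the mixed model.

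What is at stake is precision on the benefit side of the trade-off. Section 11.1 accepts a higher recurrence probability in exchange for avoiding the side effects of node dissection, so function and quality of life have to show what is gained. That comparison rests on 120 versus 60 women, and the protocol states no power for it. In an open-label trial, fixing the covariates in advance also removes a later choice among models.

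**Working it through.** **The plan's own figure.** The only power-type statement is in Section 11.1 and concerns recurrence: a 0.85 probability of declaring safety at N=120 and under 2% false early stopping, if the true rate is 3%. With pilot-informed priors that give the stated stopping boundaries, such as Beta(1.5, 31.5), success means at most 5 of 120. Then P(X ≤ 5 | 120, 0.03) = 0.847, and the probability of hitting a stopping boundary is 0.018. The figure reproduces, but it says nothing about the outcomes discussed here.

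**Inputs.** From the protocol: 120 women on ultrasound monitoring, 60 on node dissection, a five-level item, and baseline collected. Assumed: 65% versus 45% back to usual activities, two-sided 5% test, and a correlation rho between latent normal baseline and follow-up values from 0.2 to 0.7.

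**Unadjusted power by formula.**
- Pooled proportion = (0.45×60 + 0.65×120)/180 = 105/180 = 0.583.
- Null SE = √[0.583×0.417×(1/60 + 1/120)] = 0.0780.
- Alternative SE = √[0.45×0.55/60 + 0.65×0.35/120] = 0.0776.
- Power = Φ[(0.20 − 1.96×0.0780)/0.0776] = Φ(0.61) = 0.73. Simulation gives 0.72 to 0.74.

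**Adding the baseline item.** Logistic regression was simulated with and without the five-level baseline (6,000 runs per row; Monte Carlo error of each power about 0.6 points). For the responder outcome, change = follow-up − baseline was dichotomised to the same 65% versus 45%.

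| rho | 8-week item: without → with baseline | gain (points) | change outcome: without → with baseline | gain (points) |
|---|---|---|---|---|
| 0.2 | 0.720 → 0.727 | 1 | 0.723 → 0.824 | 10 |
| 0.3 | 0.722 → 0.747 | 2 | 0.731 → 0.817 | 9 |
| 0.4 | 0.723 → 0.770 | 5 | 0.726 → 0.805 | 8 |
| 0.5 | 0.732 → 0.797 | 6 | 0.723 → 0.785 | 6 |
| 0.6 | 0.735 → 0.829 | 9 | 0.724 → 0.773 | 5 |
| 0.7 | 0.733 → 0.864 | 13 | 0.720 → 0.748 | 3 |

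Other rates give a similar pattern for the 8-week item: about 0 to 15 points for 40% versus 60%, and about 1 to 14 for 50% versus 70%, over the same range of rho.

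**Why change outcomes gain too.** Having baseline in the definition of change does not remove its influence. With equal variances, corr(change, baseline) = (rho − 1)/√[2(1 − rho)] = −√[(1 − rho)/2], which is −0.50 at rho 0.5 and −0.39 at rho 0.7. The gain is therefore larger at low rho, the reverse of the 8-week item. About 3 to 8 points covers rho from 0.7 down to 0.4; below that it is slightly more.

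**Strata.** The protocol gives no prognostic strength of depth of invasion, HPV status, Charlson index or cell type for quality of life. No gain can be computed for them. Their case is consistency with the design.

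**Cost in parameters.** Main effects for the strata need 2 + 1 + 1 + 1 = 5 coefficients. With treatment and baseline entered linearly the model has 7. At the assumed rates there are 105 women with the outcome and 75 without, so 75/7 ≈ 11 of the less frequent category per coefficient. That is workable here, but not when events are few or a stratum is nearly empty.

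**The case against.** The strongest objection is that the text is silent rather than wrong. It excludes no covariate, logistic regression can carry covariates, and the list for a secondary model is commonly settled in the SAP. This stands to the extent that a reader might infer that the protocol prescribes an unadjusted analysis, and it does not say so. What remains is that the protocol did not leave adjustment wholly to the SAP: it names it for one model and omits it for the adjacent one. That difference invites the narrower reading.

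Second, the outcome is not the trial's primary endpoint. Despite the label in Section 8.1, Section 5.5 makes groin nodes primary and Section 5.6 lists quality of life as secondary. No power is claimed for it, so no stated operating characteristic is wrong. This stands and limits the weight of the point.

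Third, a reader might extend the criticism to the PROM mixed model because that sentence does not name baseline as a covariate. The text does not support this. A repeated-measures model can take baseline as a covariate or as a response, and nothing indicates that it is discarded.

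Fourth, it might be said that responder outcomes already contain baseline and so cannot gain from it. The correlation between change and baseline shows otherwise.

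Fifth, five stratum coefficients may be unstable with sparse cells. This stands, and the fix has to provide for it.

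**Conclusion.** The point holds as a modest, inexpensive improvement to Section 11.2.2. The logistic comparisons are stated without any adjustment while the adjacent model is stated with it, and the covariates will be available without new data collection.

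Under the assumed 65% versus 45% with 120:60, the baseline item adds about 1 to 13 points of power for return to usual activities over rho 0.2 to 0.7, about 6 at rho 0.5. For dichotomised change from baseline it adds about 3 to 8. The rates, test level and correlations are assumptions; none is in the protocol.

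A reader might infer a fixed loss of around 8 to 14 points. The documents do not support that. For the 8-week item, gains of that size need rho of about 0.6 to 0.7, and at rho 0.3 the gain is only 1 to 3 points across the rates tried. Nor can any part of the gain be credited to the strata.

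**What to change.** In Section 11.2.2, and in the SAP when it is written, state the following.

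- Each logistic model (return to usual activities at 8 weeks; clinically relevant PROM change at each time point) includes the baseline value of the same item or scale and the stratification factors as main effects.
- When events are few or a stratum is sparse, stratum levels are pooled or dropped by a rule set in advance. The exact test remains the last fallback.
- A marginal risk difference with its confidence interval is reported from the same model, alongside the odds ratio.

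The cost is wording only, with no new data or visits. The odds ratio becomes conditional on the covariates, which the marginal risk difference offsets for readers, and the model carries a few more parameters.

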11.2.3 Morbidity of Intervention

Post-surgery, patients will be assessed daily until discharge from hospital. Perioperative outcomes including duration of surgery (time from skin incision to wound closure), length of hospital stay,

estimated intraoperative blood loss, requirements for blood transfusions, intraoperative complications, and crossovers (including the clinical necessity for a comprehensive LND) will be recorded. Intraoperative injuries, postoperative AEs and SAEs will be recorded according to the CTCAE V5.0, at predefined time points for up to 12 months. We will compare the incidence of (a) intraoperative; (b) postoperative; and (c) serious AEs at 8 weeks and 6 months and 12 months post-surgery.

11.2.4 Lower Limb Lymphoedema

Lymphoedema will be self-assessed using validated questionnaires successfully used in our previous studies [16]. We will use our previously developed self-reported lymphoedema tool (questions on swelling in legs, pelvis or vulvar; 14 lower-limb symptoms including pain, tingling, weakness) to analyse lymphoedema at 8 weeks, and 6 months, and 12 months.

We will compare the prevalence of subjective symptoms of lymphoedema over time using a general linear mixed modelling approach. Similar analyses will be conducted on the subgroup of patients for whom we have objective assessment of lymphoedema (using leg measurements).

11.2.5 Determine the Clinical Accuracy of Preoperative, Standardised, High-Resolution Ultrasound to Identify Vulvar Cancer Patients with Positive (Involved) Groin Nodes

In women who receive a groin LND, overall ultrasound assessment scores will be compared to histopathology of the groin nodes. Sensitivity, specificity, positive and negative predictive values of the ultrasound outcomes compared to histopathology, will be evaluated together with receiver-operating characteristic.

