5.4 Secondary Objective

1. Compare Patient Reported Outcomes (PROMs) and Health Related Quality of Life (HRQL) between the groups
2. Compare pain and adverse events (AEs) (morbidity) between the groups
3. Compare incidence of lower limb lymphoedema at 12 months post-surgery between the groups
4. Compare cost and cost effectiveness between all groups
5. To assess the role of molecular biomarkers to accurately determine the burden of disease (positive lymph nodes) in vulvar cancer, assist with risk stratification and aid disease surveillance
6. Determine the diagnostic accuracy of pre-operative, standardised high-resolution groin ultrasound to identify groin node metastasis.

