5.6 Secondary Endpoint

1. HRQL and PROMS as measured by the EQ-5D and FACT-V at baseline, 8 weeks, 6 months, and 12 months
2. Morbidity at 12 months after surgery
3. Lower limb lymphoedema: incidence up to 12 months after surgery
4. Cost and cost effectiveness at 12 months post-surgery
5. Clinical accuracy of high-resolution ultrasound to predict groin lymph node involvement
6. Disease-free survival (DFS) and overall survival (OS)
7. Utility of biomarkers to reliably reflect the presence or absence of positive groin lymph nodes
8. Explore novel biomarkers for vulvar cancer

6. Study Design

A phase II, open label, multicentre, three-group, randomised clinical trial (ANVU).

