6.4 Randomisation

Eligible participants will be required to provide signed informed consent before being enrolled. Prior to enrolment, each patient will be screened for eligibility according to the inclusion and exclusion criteria. Participants will then receive a bilateral groin node ultrasound, participants who are found to have negative groin nodes will be randomised using a secure online randomisation system 2:1 to groin USM vs standard groin LND:

- ~120 participants will receive radical wide local excision or radical vulvectomy with serial high-resolution bilateral groin USM every 2 months in conjunction with clinical examinations every 3 months (groin lymph nodes are NOT removed).
- ~60 participants will receive radical wide local excision or radical vulvectomy with groin LND (Based on local clinical practice management guidelines.: either a SNB or an IFL).

Randomisation will be stratified by:

- Clinical stage
 - Depth of invasion (1-2 mm)
 - Depth of invasion (2.1-3 mm)
 - Depth of invasion 3.1 + mm
- HPV status
 - HPV positive
 - HPV negative
- Charlson Comorbidity Index ($<$ 5, \geq 5)

- Histological cell type
 - SCC
 - All other cell types (i.e. adenocarcinoma, melanoma).

Participants with a groin node ultrasound that is suspicious/indeterminate will not be randomised but receive standard groin LND (SNB or IFL as appropriate, as per institutional guidelines).

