8.3 Lymphoedema Assessment

Lymphoedema will be self-assessed using validated questionnaires successfully used in our previous studies [16]. Where trained staff and appropriate equipment are available at sites, a subset of participants will have leg circumference measured as per the standard measurement protocol provided by the Australasian Lymphology Association, measuring every 10cm from the heel working proximally. The sum of leg circumferences will be calculated and compared to pre-treatment measurements. In clinical practice, an increase by 5% or more in those measurements is considered indicative of lymphoedema development, leading to initiation of treatment. If the increase is less than 5%, the participant is observed before initiating treatment. Also, when possible, the ImpediMed SOZO BIS device will be used to assess electrical impedance to extracellular fluid in the upper and lower limbs. As per the SOZO standard protocol, lymphoedema is indicated when the right or left ratio of impedance of the upper and lower limb exceeds one standard deviation of mean ratio from normative data. When this threshold is exceeded, referral to treatment will occur. Lymphoedema will be assessed at baseline, 8 weeks, 6 months, and 12 months after surgery.

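### Lower limb lymphoedema is defined as incidence to 12 months, but section 11.2.4 analyses symptom prevalence at post-surgery visits, so the stated analysis does not estimate the stated endpoint

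*Protocol*

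**What the plan says.** Section 5.6 lists the endpoint as "Lower limb lymphoedema: incidence up to 12 months after surgery", and the synopsis agrees. The matching objective in section 5.4 is "Compare incidence of lower limb lymphoedema at 12 months post-surgery between the groups".

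The analysis is in section 11.2.4. A self-report tool covering swelling and 14 lower-limb symptoms is used "to analyse lymphoedema at 8 weeks, and 6 months, and 12 months", and then: "We will compare the prevalence of subjective symptoms of lymphoedema over time using a general linear mixed modelling approach". Similar analyses are planned for the subgroup with leg measurements.

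Baseline is collected. Section 8.3 states: "Lymphoedema will be assessed at baseline, 8 weeks, 6 months, and 12 months after surgery". For the leg measurements it is also used: "The sum of leg circumferences will be calculated and compared to pre-treatment measurements".

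Section 11.2.2, whose heading includes lymphoedema, gives a rule for yes/no outcomes: "Logistic regression will be used to compare groups on categorical outcomes (or an exact test if there are few events"). The examples that follow are return to usual activities and clinically relevant change in patient-reported scales. Lymphoedema is not among them.

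**The concern.** Incidence counts women who were free of lymphoedema before surgery and then develop it. Prevalence at a visit counts every woman who is symptomatic on that day: it includes those symptomatic before surgery and misses those whose symptoms came and went. Section 11.2.4 fixes the second quantity where the endpoint fixes the first, and no section expressly states an incidence analysis.

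The model wording adds a second question. A linear model with one common variance does not suit a yes/no outcome when the arms have different risks and different sizes.

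Lymphoedema is a large part of the benefit side of this trial. Section 11.1 accepts a 6% recurrence probability under monitoring in exchange for avoiding the side-effects of dissection. Section 8.5 plans a decision aid that gives patients outcome probabilities, lymphoedema among them. A prevalence contrast is not the probability of developing lymphoedema under each option.

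**Working it through.** The protocol gives no power, effect size or interval for lymphoedema, so there is no planned figure to reproduce.

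**1. Endpoint against analysis**

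| | Endpoint and objective (5.4, 5.6) | Analysis (11.2.4) |
|---|---|---|
| Quantity | Incidence | Prevalence |
| Time | To 12 months | At 8 weeks, 6 and 12 months |
| Baseline | Needed to identify new cases | Not mentioned |

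**2. Effect of pre-surgery symptoms**

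Let *b* be baseline prevalence, equal in both arms by randomisation. Let *i* be the new-onset risk in women free at baseline, and *s* the fraction of baseline cases still symptomatic at 12 months. If new cases are still present at 12 months, the prevalence difference (LND minus USM) is

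(1 − b)(i_LND − i_USM) + b(s_LND − s_USM).

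If baseline cases persist equally in both arms, the second term is zero and the incidence difference is multiplied by (1 − b). With assumed new-onset risks of 60% and 10%:

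- b = 10%: 0.90 × 50 = 45 points
- b = 20%: 0.80 × 50 = 40 points
- b = 30%: 0.70 × 50 = 35 points

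If s differs between the arms as much as i does, there is no dilution. The documents give neither b nor s nor a USM risk. The 60% in section 3.3 is life-long swelling after dissection, not 12-month new onset. These figures therefore show the mechanism and are not an estimate.

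**3. Visit prevalence against ever affected**

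In a simulation of 10,000 trials with three yes/no visits (latent correlation 0.7) and constant prevalence of 60% vs 10%, the proportions affected at any visit are 77.9% and 18.9%. That is a difference of 59 points, against 50 for 12-month prevalence. At 91% vs 45% the order reverses: 33 against 46 points. The gap has no fixed direction.

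**4. Standard error if 'general linear' is literal**

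The allocation is "will be randomised using a secure online randomisation system 2:1 to groin USM vs standard groin LND", with 120 and 60 women. With v = p(1 − p):

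- Common-variance SE = √[ (60·v_LND + 120·v_USM)/180 × (1/60 + 1/120) ]
- Binomial SE = √[ v_LND/60 + v_USM/120 ]

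For 60% vs 10%:

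- Common variance: (60 × 0.24 + 120 × 0.09)/180 = 0.140, so SE = √(0.140 × 0.025) = 0.059.
- Binomial: √(0.24/60 + 0.09/120) = √0.00475 = 0.069.
- Ratio 0.858. Coverage of the nominal 95% interval is 2Φ(1.96 × 0.858) − 1 ≈ 91%.

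| LND vs USM | Common-variance SE | Binomial SE | Coverage |
|---|---|---|---|
| 60% vs 10% | 0.059 | 0.069 | 91% |
| 60% vs 30% | 0.074 | 0.076 | 94.5% |
| 25% vs 5% | 0.049 | 0.059 | 89% |
| 91% vs 45% | 0.069 | 0.059 | 98% |

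The LND values 60% (section 3.3), 25% and 91% (section 3.4) are background figures. All USM values are assumed. Simulated linear mixed models agree: about 90% coverage at 60% vs 10%, 88% at 25% vs 5% and 98% at 91% vs 45%. With arm-specific variance, coverage at 60% vs 10% is 95%.

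**The case against.** Four replies have weight.

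- **The binary rule may already apply.** Section 11.2.2 names lymphoedema in its heading, offers logistic regression or an exact test, and introduces its list of outcomes as non-exhaustive. This softens the point. But lymphoedema has its own section with a different method, and a reader following that section would not fit the logistic model.
- **'General' may be a slip for 'generalised', and the section also covers leg measurements.** Summed circumference is continuous, so a linear mixed model suits it. Section 11.2.4 states no distribution, link or variance structure. The standard-error part is therefore conditional.
- **Baseline is not excluded.** Listing outcome visits does not rule out baseline as a covariate, and section 11.2 defers to an analysis plan using the estimand framework. That covers covariate detail. It does not cover a target quantity that the protocol states in two incompatible ways.
- **The primary decision concerns groin recurrence**, and this is one of several secondary endpoints.

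Two stronger readings are tempting. A reader might infer that pre-surgery symptoms bias the comparison. They do not: randomisation balances them in expectation, so the prevalence difference is a valid contrast between arms, only of a different quantity. A reader might also infer that the intervals will be too narrow. The documents do not support a direction: the interval is close to nominal at 60% vs 30% and too wide at 91% vs 45%. Even at 60% vs 10%, the 50-point difference is 0.50/0.069 = 7.3 binomial standard errors from zero, so no conclusion would change there.

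**Conclusion.** The mismatch stands on the text alone: the endpoint and objective are incidence to 12 months, and the only lymphoedema-specific analysis is of symptom prevalence at post-surgery visits, without baseline in the case definition. Followed as written, section 11.2.4 does not estimate the endpoint in section 5.6. Persistent pre-surgery symptoms would dilute the prevalence difference relative to incidence. The amount cannot be fixed from the documents, because baseline prevalence, persistence and monitoring-arm risk are not given.

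The standard-error problem is conditional on a literal 'general linear' model for a yes/no outcome. Under assumed monitoring-arm risks, coverage then runs from about 89% to about 98%, depending on which arm has the larger variance. If 'generalised' was meant, this part falls away and the endpoint mismatch remains.

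The point is worth correcting before results are seen, because lymphoedema is central to the case for monitoring. It does not touch the primary safety decision.

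**What to change.** In section 11.2.4:

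1. Make the main analysis first lymphoedema by 12 months among women without it at baseline, with the self-report case definition stated. Compare the randomised arms by logistic regression, as section 11.2.2 already does for categorical outcomes, or by a risk difference, adjusted for the stratification factors where event numbers allow.
2. Analyse visit-wise status with a generalised linear (logistic) mixed model or GEE that includes baseline status.
3. Keep the linear mixed model for continuous leg measurements, and symptom prevalence as supportive.

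The cost is wording and a standard model; baseline and follow-up assessments are already scheduled. The small downside is that women with lymphoedema at baseline leave the incidence analysis. At an assumed 10% baseline prevalence, 108 and 54 women would remain of 120 and 60. Because this restriction uses a pre-randomisation characteristic, the randomised comparison is preserved.
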